Date: Approved Last on November 22, 2022

Title: Comparing Brief Relaxation period to Virtual Reality period in reducing dental anxiety prior to root canal treatment; a randomized control trial

NCT #: 05720897

Methods Protocol

Inclusion Criteria

In order to participate in the study, patients must have been between the ages of 18 to 90 years old and have the capacity to independently give consent for root canal treatment. The participant must have been proficient in English and have no visual or hearing impairments that would interfere with listening with earphones or utilizing virtual reality glasses. Subjects must also need non-surgical root canal treatment.

Exclusion Criteria

Subjects may not have participated in the study if they have a history of vertigo or severe motion sickness. They must not have required nitrous oxide sedation, nor pharmacologic anxiolytics or sedatives for treatment. In addition, self-reporting of any severe psychiatric disease, medical history of seizures, concussions, or severe neurological conditions, visual and hearing impairments, and reporting of a cardiac pacemaker or defibrillator, would rule out patients from this study.

Materials

The project will require the following: Oculus Quest2 (*Meta Quest; Meta2 VR Headset*); Maxwell 190319 Stereo Headphone, Black (*Amazon*), Dell Optiplex 7050 Computer, ComfortCuff 506N3 Series (*Criticare Systems Inc.*).

Sample Size

With a sample size of 28 patients per group completing the study, the study will have an 80% power to detect changes in the patient's self-reported anxiety as measured by their responses to the psychometrically validated STAI instrument of 3.6 (within each group an effect size of 0.55) and differences of a 5.0 between groups (an effect size of 0.77). The calculations are based on paired and two-sample t-test calculations, respectively, and these calculations assume a within-group standard deviation of 6.5 for change in STAI and a two-sided 5% significance level. To account for a 5% dropout rate, 30 patients will be enrolled per group.

Methodological Procedures for Relaxation Interventions: ABR vs RVR

Institutional Review Board (IRB) submission was secured after an internal Research Committee first gave approval of study.

Auditory Brief Relaxation (ABR)

This study's brief relaxation period consisted of an 8 minute ABR with 90 seconds of relaxing background music, five-minutes of an audio recording performed by a Certified Health and Well-being Coach and Qualified Teacher of Mindfulness-Based Stress Reduction and ending with another 90 seconds of relaxing outgoing music. The recording consisted of suggestive elements for how the patient can reduce their anxiety in real-time. The guided relaxation lasted approximately five minutes and involved the patient focusing on their scanning their body for tension and diaphragmatic breathing.

Relaxation Virtual Reality (RVR)

The VR headset used for this project was headset by Meta 2. The experience involved a nonmotive and noninteractive virtual reality experience. Patients required a very brief training on how to place and adjust the headset for comfort and volume, and a glass of water was available within arm's reach. Controllers were not distributed to participants for the RVR to be more uniform and to avoid an interactive, gamification experience. The standardized app that was presented during the RVR session was NatureTrek App (*GreenerGames*). In this program, the participant choose and immersed themselves within one of 11 themed for approximately 8 minutes to align with the comparative relaxation time of the ABR group and to increase the likelihood that the patient experiences a sense of immersion and presence. Examples of the scenes included savannah, beach, meadow, and space. If there were any technical or health related issues during the experience, a trained dental assistant or endodontic dental resident will be always in sight of participants.

Recruitment and Enrollment of Experimental Subjects & Protocol for Data Collection

Candidates for the study were selected from patients that were scheduled in graduate endodontic clinic for evaluation of non-surgical root canal therapy (NSRCT). A biostatistician randomized 60 participants for the study to split participants between Audio Alone Relaxation (ABR) and Relaxation Virtual Reality (RVR). The randomization list was generated using R statistical software to randomly assign participants equally to the two groups, using a block randomization to ensure group balance throughout study enrollment. The researcher and a

Clinical Research Coordinator worked together to administer randomized assignments. This is a non-blinded study in such that both researcher and Clinical Research Coordinator knew the type of intervention being provided to which participant. Either the Clinical Research Coordinator or researcher acquired written, informed consent for enrollment of patients into the study, and the patient's age and gender. There was no initiative or incentive for patients willing to participate in the study. Once consent was obtained and all related questions answered, the investigator, delivered either the placement of headphones for a brief auditory relaxation period (ABR) of five minutes, or the use of relaxation virtual reality (RVR) using a VR headset. Both of these interventions were applied after consent and just prior to administration of local anesthetic. There were three data collection points in which evaluations were conducted. At T0 prior to the beginning of endodontic treatment, the following measurements were conducted: (1) Vitals were recorded for blood pressure and heart rate (2) patient's perceived anxiety was evaluated by having patients complete State-Trait Anxiety Indicator (STAI) and (3) a verbal response was requested of the patient using a Visual Analog Scale (VAS). VAS was used as a complementary measure as well as an effective stand-alone measure. T1 data collection occurred approximately 10 minutes after T0 and after the aforementioned intervention of the ABR or RVR in which (1) the patient's blood pressure (BP), and heart rate (HR) were taken and (2) a response given to the VAS. Finally, at T2 which is after the completion of the endodontic treatment inclusive of the final radiograph, once again the (1) BP and HR was collected (2) the STAI was completed and (3) the response to VAS again completed. \

Informed Consent

All subjects were required to read, acknowledge they understood, and sign a document of informed consent before they could participate in the study. The subject received a copy of the consent form.

Study Procedure and Protocol: Timeline

1. After patient is brought back to the operatory and verbal introductions, rapport building, and agenda setting has occurred then the patient's medical history is reviewed which is the standard of care for endodontic treatment.
2. The patient was invited to participate in the study during the evaluation of the patient's dental needs. During the reading of the consent process, the researcher

reviewed with the patient all related inclusion/exclusion criteria for this study in order to first determine if the participant might qualify for the study.

3. The researcher verbally reviewed and got written consent for both the Non-surgical Root Canal Therapy (NSRCT) – {standard of care procedure} and the research study.
4. If the subject qualified, the participant was selected randomly to be a part of the RVR or ABR group, as per the randomization sheet.
5. *T0*: Blood pressure and heart rate recordings were recorded by the student investigator & STAI and VAS completed by participant.
6. Intervention: VR headsets or earphones with AAR were applied by the investigator and the patient experienced the intervention (approximately 8 minutes).
7. *T1*: VAS completed by participant and BP & HR are recorded.
8. Administration of local anesthesia and non-surgical root canal therapy performed by endodontic resident and timer began for treatment.
9. *T2*: STAI, VAS, BP, HR all recorded at the end of the appointment which was after final radiograph.
10. Dismissal of patient and treatment stops. In order to test both study hypotheses, repeated measures of ANOVAs will be conducted to test for any changes in time across T1, T2, and T3 for STAI and VAS Scores, BP and HR within the ABR and RVR groups and to compare between the two groups. In addition, associations of the outcomes with socio-demographic and related factors data will be tested by adding these factors as covariates in additional repeated measures of ANOVAs. Specific socio-demographic and related factors data to be collected will include: Age, gender, race/ethnicity, previous experience with auditory relaxation and relaxation by virtual reality and length of time for endodontic treatment. Two-sided 5% significance levels will be used for all inferential statistical analyses.

Statistical Analysis

With a minimum sample size of 28 patients per group (ABR Group; n=30 & VRR Group; n=28) having completed the study, the study has an 80% power to detect changes in patient's self-reported anxiety as measured by their responses to the psychometrically validated STAI instrument of 3.6 within each group (with an effect size of 0.55) and differences of a 5.0

between groups (with an effect size of 0.77). The calculations are based on paired and two-sample t-test calculations, respectively, and these calculations assume a within-group standard deviation of 6.5 for change in STAI and a two-sided 5% significance level.

Chi-square tests and two-sample t-tests were used to compare the two groups by differences in demographic characteristics. Due to non-normality of the outcomes, Wilcoxon Signed Rank tests were used to test for changes in the outcomes over time within each group, and Mann-Whitney U tests were used to compare the outcomes between the two groups at each time. Additional exploratory analyses to evaluate the associations of demographic characteristics with changes in the outcomes were performed using cumulative logistic regression. A two-sided 5% significance level was used for all tests. Analyses were performed using SAS version 9.4 (SAS Institute, Inc., Cary, NC, USA).

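### The head-to-head STAI comparison has no planned estimate or confidence interval, and the rank tests at each time do not test the change in STAI on which the trial was sized

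*Combined protocol and SAP*

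**What the plan says.** The title sets up a comparison of two interventions, and both arms receive active relaxation. The Sample Size section states "With a sample size of 28 patients per group completing the study, the study will have an 80% power" for two effects on STAI: "3.6 (within each group an effect size of 0.55) and differences of a 5.0 between groups (an effect size of 0.77"). It adds that "The calculations are based on paired and two-sample t-test calculations, respectively", and that they "assume a within-group standard deviation of 6.5 for change in STAI and a two-sided 5% significance level". The Statistical Analysis section repeats these figures and gives 30 completers for ABR and 28 for the virtual reality arm.

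Two places describe how the arms are compared:

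- **Statistical Analysis:** non-normality is given as the reason for rank methods, and "Mann-Whitney U tests were used to compare the outcomes between the two groups at each time". Within-arm changes are tested by Wilcoxon signed-rank tests.
- **Study Procedure and Protocol: Timeline, item 10:** repeated-measures ANOVAs are to test change over time within the arms and to compare the arms, with covariates added in further models.

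Neither names a between-arm effect measure, a confidence interval, an equivalence or non-inferiority margin, or a rule for reading a non-significant result. STAI is collected at T0 and T2 only. VAS, blood pressure and heart rate are collected at T0, T1 and T2.

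**The concern.** There are two gaps between the question and the stated analysis.

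First, the sized quantity is not the tested one. The SD of 6.5 and the 5.0-point difference refer to change in STAI. A Mann-Whitney test at each time compares raw STAI scores at T0, where any difference is a chance imbalance, and again at T2, with no allowance for T0. No between-arm test of change appears in the Statistical Analysis section.

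Second, a rank test without an estimate gives only a p-value. Suppose both arms fall significantly and p exceeds 0.05 between them. The arms may be close, or the data may be too few to separate them, and the stated outputs do not say which. At stake is the answer to the title question, the one question here that rests on randomisation.

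**Working it through.** **Inputs.** From the Sample Size section: 28 completers per arm, SD of change 6.5, two-sided 5%, a paired t-test within arm and a two-sample t-test between arms, and effects of 3.6 and 5.0. From the Statistical Analysis section: actual completers 30 and 28.

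**1. Reproduce the plan's figures.** Power comes from the noncentral t distribution.

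- Effect sizes: 3.6/6.5 = 0.554 and 5.0/6.5 = 0.769, as stated up to rounding.
- Within arm: noncentrality 0.554 × √28 = 2.93, df 27, power 80.7%.
- Between arms: standard error 6.5 × √(1/28 + 1/28) = 1.737, noncentrality 5.0/1.737 = 2.88, df 54, power 80.7% (82.0% at 30/28).
- Dropout: 28/0.95 = 29.5, so 30 enrolled.

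All the stated figures hold.

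**2. Between-arm power at smaller differences (two-sample t, SD 6.5).**

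| True difference in change | Power, 28/28 | Power, 30/28 |
|---|---|---|
| 5.0 | 81% | 82% |
| 3.6 | 53% | 54% |
| 1.8 | 17% | 18% |

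The value 3.6 is used because it is the plan's own within-arm figure, and 1.8 is half of it. Neither is a predicted difference. A simulated Mann-Whitney test on normally distributed changes (10,000 replicates, 28/28) gives 78%, 51% and 17%, so the choice of test hardly alters the picture.

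**3. Expected precision.** Half-width = t(0.975, df) × 6.5 × √(1/n₁ + 1/n₂).

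- 28/28: 2.005 × 1.737 = 3.48 points.
- 30/28: 2.003 × 1.708 = 3.42 points.

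**4. What an interval would add.** If the arms are truly identical and changes are normal with SD 6.5, the 95% interval lies wholly inside ±5.0 in about 61% of trials at 28/28 and 64% at 30/28 (simulated, with the SD estimated from the data). In such a trial a difference as large as the planned 5.0 could be set aside. The p-value alone would not show this.

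**5. Tested against sized quantity.** The documents give no SD for the T2 score. Assume equal SDs at T0 and T2 and a correlation ρ between them. Then the T2 SD = 6.5/√(2(1 − ρ)).

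| ρ (assumed) | T2 SD | 95% half-width, 28/28 | Power for 5.0 |
|---|---|---|---|
| 0.3 | 5.5 | 2.9 | 92% |
| 0.5 | 6.5 | 3.5 | 81% |
| 0.7 | 8.4 | 4.5 | 59% |

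The stated 80% therefore carries over to a comparison of T2 scores only if ρ is near 0.5 or lower, which the documents do not address. The table uses the t-test as a guide to the rank test.

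**The case against.** The best defence is that the plan contains no error of calculation and claims nothing improper. Four parts of it stand.

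- **The 5.0 and 3.6 figures are compatible.** A reader might infer that a 5.0-point between-arm target contradicts a 3.6-point within-arm one. It does not. With equal arms and a common SD, the two-sample standard error is √2 times the paired one, and 3.6 × 1.41 = 5.1. Both figures state what 28 per arm can detect. Neither is a forecast, and nothing caps the change in an arm at 3.6.
- **The power sentence needs no correction.** It already ties 80% to a 5.0-point difference.
- **No similarity margin exists.** A reader might treat 3.6 as the limit within which the arms count as similar and conclude that the trial could almost never show similarity. The documents offer 3.6 only as a detectable within-arm change, so that conclusion has no basis in them. Against 5.0, the plan's own between-arm figure, an interval would often be informative, as step 4 shows.
- **Silence is not refusal.** The Statistical Analysis section names tests; it does not say that only p-values will be reported, and no equivalence claim is made. Item 10 also names an ANOVA that compares the arms.

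None of this closes the gap. Item 10 specifies no estimate or interval either, the later section departs from it because of non-normality, and nothing commits the authors to reporting how large the between-arm difference is.

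**Conclusion.** The point holds as a gap in analysis and reporting, not as a fault in the sample size. The Statistical Analysis section compares the arms on a quantity other than the one sized. Neither it nor item 10 promises an estimate with an interval. At the planned SD of 6.5, power is about 53% for a 3.6-point difference and 17% for 1.8, and the expected 95% half-width is about 3.5 points (3.4 at 30/28). A non-significant result is thus quite possible even when the arms differ by several points, and a bare p-value would leave it unexplained. These figures assume approximately normal changes and a common SD of 6.5. The document itself reports non-normal outcomes, so they are a guide to scale. The tests named are valid as tests, so the importance is moderate. It is nevertheless worth acting on, because it concerns the trial's main question and the remedy is easy.

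**What to change.** 1. Make the main between-arm result the difference in T0-to-T2 STAI change with its 95% confidence interval. If rank methods are kept, use the Hodges-Lehmann shift of the changes with its interval, and apply the Mann-Whitney test to the changes.
2. Do the same for change from T0 in VAS, blood pressure and heart rate.
3. Reconcile item 10 of the Timeline with the Statistical Analysis section, so that one method is named for the comparison of arms and the reason for the switch is given once.
4. State that p>0.05 between arms will not be read as evidence that they are equally effective, and that the interval will be used to say which differences remain compatible with the data.

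The cost is a few lines of SAS on changes that the within-arm tests already use, and an interval that may look wide. No further patients are needed. The Statistical Analysis section is already in the past tense with completers counted, so the added analysis should be labelled as such and not presented as prespecified.

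### Nothing in the plan keeps the treating resident unaware of the arm, so the T2 comparisons, including STAI, are open to operator-related bias of unknown size

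*Combined protocol and SAP*

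**What the plan says.** All references are to the Combined protocol and SAP.

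- **Relaxation Virtual Reality (RVR):** as cover for technical or health problems during the headset session, "a trained dental assistant or endodontic dental resident will be always in sight of participants". The section on the audio arm names no observer.
- **Recruitment and Enrollment:** the study is declared open in the sense that "both researcher and Clinical Research Coordinator knew the type of intervention being provided to which participant". The treating operator is not mentioned. On timing, "Both of these interventions were applied after consent and just prior to administration of local anesthetic".
- **Timeline, step 3:** the researcher obtains consent for the root canal as well as for the study.
- **Timeline, steps 6 and 7:** the investigator applies the device; VAS, blood pressure and heart rate are then taken at T1. STAI is not.
- **Timeline, step 8:** "Administration of local anesthesia and non-surgical root canal therapy performed by endodontic resident and timer began for treatment".
- **Timeline, step 9:** "STAI, VAS, BP, HR all recorded at the end of the appointment which was after final radiograph".
- **Sample Size:** the power statement concerns change in STAI only.

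**The concern.** Patients cannot be blinded to a headset or headphones, nor can the person who fits them. The operator is different: the device is off and T1 is recorded before the anaesthetic is given, so the plan's own order of events would allow the operator to be kept unaware. The plan makes no use of this, and in the VR arm it allows an endodontic resident to watch the session.

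The whole dental procedure lies between the intervention and the second STAI. An operator who knows the arm could, without intending to, vary reassurance, pace or communication. At T2 such a difference could not be told apart from a lasting effect of VR or audio. Randomisation does not protect against differences that arise after allocation, and adjusting for baseline or for treatment length would not remove them.

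**Working it through.** **1. Can the observer and the operator be the same person?** The RVR section allows either an assistant or an endodontic resident to watch. Timeline step 8 has an endodontic resident treat. No sentence separates the two roles or equates them, so the overlap is permitted but not stated. Step 3 leaves a second opening: the researcher, who knows the arm, takes consent for the root canal, and nothing says that the researcher never treats.

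**2. Is operator awareness addressed anywhere?** No. The statement on blinding names two roles, the researcher and the coordinator.

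**3. Which outcomes are exposed?**

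| Time | Measures | Relative to operator's treatment |
|---|---|---|
| T0 | STAI, VAS, BP, HR | before |
| T1 | VAS, BP, HR | before |
| T2 | STAI, VAS, BP, HR | after |

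On this schedule, change in STAI can only be T0 to T2, so it spans the treatment. This is inferred: the Sample Size section does not name the time points, and Timeline step 10 lists T1, T2 and T3, labels that do not match the schedule. All T2 measures are exposed; all T1 measures are not.

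**4. The plan's own power figure.** Inputs from Sample Size: 28 completers per group, SD 6.5 for change in STAI, two-sided 5%.

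- Between groups: 5.0 / 6.5 = 0.77; noncentrality 0.769 × √(28/2) = 2.88 on 54 degrees of freedom; power 80.7%.
- Within group: 3.6 / 6.5 = 0.55; noncentrality 0.554 × √28 = 2.93 on 27 degrees of freedom; power 80.7%.
- Dropout: 28 / 0.95 = 29.5, rounded up to 30.

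The stated 80% and the 30 per group reproduce. No figure in the plan is contested here.

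**5. Sensitivity, on assumed shifts.** The documents give no size for operator effects. Suppose arm-dependent operator behaviour moved the difference in mean STAI change by b points. With no true difference, the noncentrality is (b / 6.5) × √14; if the shift opposes a true difference of 5.0, it is ((5.0 − b) / 6.5) × √14. With the same two-sample t-test:

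| Assumed shift b (points) | Rejection rate, no true difference | Power, shift opposing a true 5.0 |
|---|---|---|
| 0 | 5.0% | 80.7% |
| 0.5 | 5.9% | 72.0% |
| 1 | 8.7% | 61.8% |
| 2 | 20.5% | 39.6% |
| 3 | 39.6% | 20.5% |

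These rows show how sensitive the test would be. They are not evidence that any such shift occurred. The Statistical Analysis section uses Mann-Whitney tests at each time instead of this t-test; the percentages would differ, but a shift at T2 would carry through to those tests too.

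**The case against.** The observer sentence is a safety provision, names an assistant as an alternative, and applies only to the VR arm. A reader might infer that the treating resident did watch the VR sessions, but no passage says so. A reader might also infer that the T2 STAI result is biased towards one arm. The documents do not support that either: both arms are active relaxation of about 8 minutes, nothing suggests that operators favoured one, and no behaviour is described as differing by arm. Neither the 5.0-point target nor the length of the procedure measures the bias. These objections stand, and they limit the point to a possible, unquantified bias.

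The study declares itself non-blinded, so there is no contradiction in the text. That is true, but the declaration does not cover the operator, and the inability to blind patients is no reason to leave an avoidable route open.

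T1 offers measures free of this route, and the title concerns anxiety before root canal treatment. This stands as a real mitigation, but STAI is not among the T1 measures.

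STAI is completed by patients who know their own arm. Blinding the operator does nothing about that, and some patients will tell the operator. Both limits are accepted. The route at issue is the operator changing the patient's experience, not the operator scoring the scale.

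Finally, much of the text is in the past tense and the Statistical Analysis section gives completed group sizes of 30 and 28. If conduct is over, the procedural change cannot alter these data; what remains is to report the limitation.

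**Conclusion.** The point holds as a design weakness. The plan permits, without stating, that the resident who performs the root canal also watches the VR session, and it does nothing to keep the operator unaware although the sequence would allow it. Arm-dependent operator behaviour is therefore a possible source of bias in every T2 comparison, including the only powered outcome. Its size and direction cannot be determined from the documents. T1 VAS, blood pressure and heart rate are not exposed to it.

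The conclusion rests on reading change in STAI as T0 to T2, which the schedule implies, and on the premise that operator conduct can affect anxiety reported after treatment, which is plausible but not shown in the documents. It does not support a claim that operators knew the arm, that they acted on it, or that the sample size calculation is wrong.

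**What to change.** 1. In both arms, make the continuous observer the trained dental assistant, an option the plan already contains for VR, or any qualified person other than the treating resident. Continuous observation is kept.
2. Have the researcher or the coordinator deliver the device, whichever of them is not treating that patient. This needs a small edit, because the Recruitment and Enrollment section and Timeline step 6 assign delivery to the investigator.
3. Do not tell the treating resident the arm, and ask the patient not to mention it.
4. Record at T2 whether the resident knew the arm, and report the T2 results with that limitation. If enrolment is complete, report what is known about operator awareness and note that the T1 measures avoid this route.

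The cost is a few protocol sentences and some scheduling effort, since the intervention comes directly before the anaesthetic. The blind will be imperfect because some patients will reveal their arm. Bias in self-reported STAI from patients' knowledge of their own arm remains.

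### STAI, the only powered outcome, is not measured between the intervention and the root canal, so its within-group change cannot be credited to either relaxation method

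*Combined protocol and SAP*

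**What the plan says.** All references are to the combined protocol and SAP.

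- **Schedule.** In Study Procedure and Protocol: Timeline, step 5 (T0) records STAI, VAS, blood pressure and heart rate. Step 7 (T1, after the intervention) has "VAS completed by participant and BP & HR are recorded". Step 8 is local anaesthesia and the root canal. Step 9 (T2) has "STAI, VAS, BP, HR all recorded at the end of the appointment which was after final radiograph". The account in Recruitment and Enrollment agrees: STAI at T0 and T2, none at T1.
- **Power.** Sample Size and Statistical Analysis give power for STAI only. They cover a change in the "STAI instrument of 3.6 within each group (with an effect size of 0.55") and a between-group difference of 5.0. Completers are given as "ABR Group; n=30 & VRR Group; n=28) having completed the study".
- **Analysis.** Step 10 plans repeated-measures ANOVA for "changes in time across T1, T2, and T3 for STAI and VAS Scores, BP and HR", within each group and between groups. On change inside each arm, Statistical Analysis states that "Wilcoxon Signed Rank tests were used to test for changes in the outcomes over time within each group". On the contrast of the two arms, the same section states that "Mann-Whitney U tests were used to compare the outcomes between the two groups at each time".
- **Arms.** Both groups receive a relaxation intervention, auditory or virtual reality. No untreated arm is described.
- **Role of VAS.** Recruitment and Enrollment states that "VAS was used as a complementary measure as well as an effective stand-alone measure".

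**The concern.** STAI has two time points, with anaesthesia, the whole root canal and the final radiograph lying between the intervention and the second one. A fall from T0 to T2 may reflect the relaxation period, the treatment, or relief that the visit is over. No arm goes without an intervention, so nothing in the trial separates these causes. The plan nevertheless powers this change and tests it in each arm, and does not say how it is to be read. A significant fall in one or both arms could then be reported as evidence that the relaxation worked, which no comparison in the trial supports.

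The title concerns anxiety before root canal treatment. A reader with that question needs the between-group comparison at T1. The only self-reported anxiety measure there is VAS, and its comparison has no stated power and is not adjusted for T0 VAS.

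Step 10 also refers to a T3 that does not exist and implies three STAI times.

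**Working it through.** **1. Which STAI change is powered**

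| Measure | T0 | T1 (after intervention) | T2 (after root canal) | Step 10 |
|---|---|---|---|---|
| STAI | yes | no | yes | T1, T2, T3 |
| VAS, BP, HR | yes | yes | yes | T1, T2, T3 |

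With STAI at T0 and T2 only, the 3.6-point change must be T0 to T2. Moving the step 10 labels back to T0, T1 and T2 does not repair the text for STAI, because its middle time is still missing.

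**2. The plan's own figures**

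Inputs from Sample Size: n = 28 per group, SD of change 6.5, two-sided 5%.

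- Within group: the paired t statistic is noncentral t with n − 1 = 27 df and noncentrality (d/SD)√n. For d = 3.6, this is 0.554 × 5.292 = 2.93, giving power 80.7%.
- Between groups: 54 df and noncentrality (5.0/6.5)/√(2/28) = 0.769/0.267 = 2.88, giving power 80.7%.

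Both match the stated 80%. The arithmetic is sound; the issue is what the within-group test can show.

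**3. Within-group test with no intervention effect**

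Assume both arms have the same T0–T2 fall, unrelated to the intervention. Its size is not in the documents, so a range is shown. For the paired t-test at n = 28, the noncentralities are 1.47, 2.93 and 4.07. The signed-rank figures come from simulation (60,000 runs, SD 6.5). The skewed changes are gamma with shape 4, in either direction.

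| Significant result | Fall 1.8 | Fall 3.6 | Fall 5.0 |
|---|---|---|---|
| Paired t, n = 28 | 29.3% | 80.7% | 97.5% |
| Paired t, n = 30 | 31.1% | 83.4% | 98.3% |
| Paired t, both arms (28 and 30) | 9.1% | 67.3% | 95.8% |
| Signed-rank, n = 28, normal changes | 27.7% | 78.3% | 96.8% |
| Signed-rank, n = 28, skewed changes | 16.6–41.1% | 74.5–82.8% | 96.5–98.1% |

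The both-arms row is the product of the two rows above it, for example 0.807 × 0.834 = 0.673.

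**4. Between-group STAI test in the same setting**

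Mann-Whitney on T2 STAI, 30 versus 28, common fall 3.6, no arm difference (40,000 runs): 4.5%, 4.8% and 4.8% significant for assumed T0–T2 correlations of 0.3, 0.5 and 0.7. The common fall cancels, so the randomised comparison is valid for anxiety at the end of the appointment.

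**5. T1 VAS between groups**

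Simulation of 30 versus 28, normal scores, 40,000 runs. The adjusted analysis regresses ranked T1 VAS on arm and ranked T0 VAS. The correlations and the 0.65 SD difference are assumptions.

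| Analysis | Difference with 80% power | Power at 0.65 SD |
|---|---|---|
| Mann-Whitney, unadjusted | 0.77 SD | 65% |
| Adjusted, r = 0.3 | 0.75 SD | 69.0% |
| Adjusted, r = 0.5 | 0.68 SD | 76.4% |
| Adjusted, r = 0.7 | 0.57 SD | 88.7% |

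The adjusted test has size 5.0–5.3%. As a rough check, 0.77 × √(1 − r²) gives 0.73, 0.67 and 0.55, close to the simulated values. With VAS rounded and bounded at 0–10 (assumed mean 4, SD 2.5), power is 64–65% unadjusted and 68.1%, 75.1% and 87.4% adjusted.

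**The case against.** - **The harm is hypothetical.** The documents contain no conclusions and do not credit the within-group change to an intervention. Step 10 refers to two study hypotheses that the text never states. This is true. But the plan powers and tests the contrast, and gives no limit on its interpretation.
- **The illustration is near-tautological.** A test with 80% power for a 3.6-point change rejects about 80% of the time whenever the mean change is 3.6, whatever the cause. That is fair: the figures show that the test cannot tell causes apart, not how large the fall will be. Part of the spread under skewness is also an artefact, since the signed-rank test rejects about 7–8% of the time at zero mean change when changes are skewed.
- **The title may describe when the relaxation is given, not when anxiety is measured.** That reading is possible, and an end-of-appointment STAI is then a legitimate outcome. The attribution problem is unchanged.
- **Baseline adjustment is a preference.** The unadjusted T1 test is valid, and at r = 0.3 the gain is only about 4 percentage points. Other planned analyses do use T0. This limits the weight of the point but does not remove it: the planned between-group comparison at T1 leaves out a baseline that was collected.
- **The data have been seen.** Completion numbers and non-normality are already reported, and a post hoc model adds flexibility where no primary outcome is named. This stands, and is why a single model should be named and labelled post hoc.
- **A T1 STAI would not have supplied a control.** Correct. It would have removed relief at completion of the procedure, but not effects of time or repeat testing.

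**Conclusion.** The concern holds, and the text should be changed. The powered within-group STAI change spans the whole root canal and has no untreated comparator, so it cannot support a claim that either intervention reduced anxiety. With no intervention effect, a common fall of 1.8 to 5.0 points would give a significant paired t-test in 29% to 97.5% of trials per arm. This assumes SD 6.5 from the plan and a fall whose size the documents do not give.

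The between-group STAI comparison is valid but describes the end of the appointment. A null result there would not show whether both methods worked or neither did. T1 VAS, supported by blood pressure and heart rate, is the evidence on anxiety before treatment. Its planned comparison reaches 80% power only at about 0.77 SD. Adjustment for T0 VAS would lower that to between 0.75 and 0.57 SD for assumed correlations of 0.3 to 0.7.

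The step 10 time labels are a wording error. The tests named in Statistical Analysis can be run with two STAI times.

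**What to change.** 1. **Step 10.** State that STAI is analysed at T0 and T2, and VAS, blood pressure and heart rate at T0, T1 and T2. This corrects the times only. The difference between the ANOVA in step 10 and the rank tests in Statistical Analysis is a separate matter.
2. **Interpretation of STAI.** Add to Statistical Analysis: *STAI results describe anxiety at the end of the appointment. Efficacy conclusions rest on the comparison between randomised groups. Within-group STAI change from T0 to T2 is descriptive and is not evidence of an intervention effect.*
3. **Anxiety before treatment.** Keep the planned T1 VAS comparison and add one analysis adjusted for T0 VAS, with its model fixed before it is run. Ranked T1 VAS regressed on arm and ranked T0 VAS suits the reported non-normality; a proportional-odds model is an alternative. Disclose that the adjustment and the added emphasis are post hoc, while the comparison itself was planned.

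The cost is a few sentences and one extra analysis of data already collected. The downside is the post hoc label on the adjustment and on the greater weight given to T1 VAS.
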